## **List of abbreviations**

AE	Adverse Event
AESI	Adverse Event of Special Interest
ATS	All treated subjects
CSR	Clinical study report
eCRF	Electronic Case Report Form
eCRS	Case Retrieval Strategy
GSK	GlaxoSmithKline
MedDRA	Medical Dictionary for Regulatory Activities
PT	Preferred Term
SAE	Serious Adverse Event
SAP	Statistical analysis plan
SMQ	Standardized MedDRA query
SoC	Standard of care

## 1. Introduction

This first amendment of the statistical analysis plan (SAP) provides detailed statistical methodology for the analyses of data which will be used for preparation of the CETB115A2X01B (study 200170) clinical study report (CSR) and is based on the study protocol amendment 01, dated 06-Apr-2016.

This is a multi-center, non-randomized, open-label, phase IV, rollover study conducted in subjects who are currently participating in a Novartis sponsored investigational study with eltrombopag (i.e. parent study such as TRC114968/ASPIRE or TRA105325/EXTEND), and are receiving clinical benefit without unacceptable toxicity.

All decisions regarding final analyses, as defined in the SAP document, have been made prior to database lock.

Last Patient Last Visit was achieved on 23-Feb-2022. In total, data of 22 subjects will be analysed.

### 1.1 Study design

This Phase IV, multicenter, non-randomized, open-label, uncontrolled, rollover study is designed to provide continued access to eltrombopag to subjects who are currently participating in a Novartis sponsored investigational study of eltrombopag (parent study), and are receiving clinical benefit without unacceptable toxicity. Enrollment into this study will be dependent upon the mutual agreement between Novartis and a site to participate in this study. Subjects will be enrolled into three cohorts (cohort A, cohort B and cohort C) based upon the disease under study in their parent study(e.g. myelodysplastic syndrome(MDS), acute myeloid leukemia(AML), idiopathic thrombocytopenic purpura(ITP) etc.).

Subjects may continue treatment in this rollover study until they are no longer receiving clinical benefit, develop an unacceptable toxicity, withdraw consent, enroll into another interventional study, or until another mechanism is available for the subject to receive eltrombopag such as compassionate use, named patient program, commercially available for the appropriate indication, etc. Subjects participating in Investigator Sponsored Studies will not be eligible to participate in this study.

**Cohort A (MDS/AML adult subjects)** will consist of adult subjects who have completed study treatment with eltrombopag during their participation in a parent study for MDS/AML (i.e. TRC114968/ASPIRE).

**Cohort B (ITP adult subjects)** will consist of adult subjects who have completed study treatment with eltrombopag during their participation in a parent study for ITP (i.e. TRA105325/EXTEND).

**Cohort C (ITP pediatric subjects)** will consist of pediatric subjects who have completed study treatment with eltrombopag during their participation in a parent study for ITP. Once a subject turns 18 years of age, they may remain in the study and follow the Cohort B guidelines. The study will consist of a Transition Visit, Study Treatment Visits, End of Treatment Visit, and a Follow-Up Visit.

Safety will be evaluated through physical exams, clinical laboratory tests (hematology and clinical chemistry), and monitoring of adverse events/serious adverse events. Additional safety assessments may be done as per standard of care (SoC) and/or when medically indicated. Assessment of clinical benefit will be performed throughout the study using local SoC as determined by the investigator to determine continued study participation and treatment with eltrombopag. Only subjects considered by the investigator to be receiving clinical benefit without unacceptable toxicity may continue on study treatment.

## **1.2 Study objectives and endpoints**

The primary objective of this study is to provide continuing treatment with eltrombopag for subjects who are currently participating in a Novartis sponsored investigational study of eltrombopag (parent study) and to collect long term safety data.

There are no formal endpoints for this study.

## **2 Statistical methods**

### **2.1 Data analysis general information**

The tables, figures and listings will be generated by Novartis programmers. SAS version 9.4 or later software will be used to perform all data analyses and to generate tables, figures and listings. Since not a single subject was enrolled to Cohort C throughout the entire trial, all tables, figures and listings will only include patients from Cohorts A and B.

The final analysis will take place after the last subject, last visit has occurred and the database has been locked. All available data will be included.

**Pooling of centers:** Unless specified otherwise, data from all study centers will be pooled for the analysis. Due to expected small size of centers, no center effect will be assessed.

**Qualitative data** (e.g., gender, race, etc.) will be summarized by means of contingency tables; a missing category will be included as applicable. Percentages will be calculated using the number of subjects in the relevant analysis set or subgroup as the denominator.

**Quantitative data** (e.g., age, body weight, etc.) will be summarized by appropriate descriptive statistics (i.e. mean, standard deviation, median, minimum, and maximum).

#### **2.1.1 General definitions**

##### **Investigational drug and study treatment**

Investigational drug, study drug and study treatment refer to eltrombopag.

Data will be presented by cohorts in applicable summaries, figures, and listings.

##### **Date of first/last administration of study drug**

The date of first administration of study drug is defined as the first date when the first non-zero dose of study drug was administered as per the Dosage Administration electronic case report

form (eCRF). For simplicity, the date of first administration of study treatment will also be referred as *start of eltrombopag*.

The date of last administration of study drug is defined as the last date when a non-zero dose of study drug was administered as per Dose Administration eCRF. This date is also referred to as *last dose of eltrombopag*.

### **Duration of exposure**

The duration of exposure is calculated as:

- Duration of eltrombopag exposure (months) =[(last dose date of eltrombopag) - (first dose date of eltrombopag) + 1]/ 30.4375.

If the start or end date of eltrombopag is missing, the duration will be missing. The duration includes periods of temporary interruption (planned or actual) for any reason.

### **Definition of Months and Years**

A month will be calculated as  $(365.25 / 12) = 30.4375$  days. Where duration is to be reported in months, duration in days will be divided by 30.4375. Where duration is to be reported in years, duration in days will be divided by 365.25.

### **Study day**

The study day *for safety assessments* (e.g. adverse event onset, laboratory abnormality occurrence, vital sign measurement, dose interruption etc.) will be calculated as the difference between the date of the event (onset date of an event, assessment date etc.) and the start of study treatment plus 1. The first day of study treatment is therefore study day 1. Example: if start of study treatment is on 05-Jan-2014 and start date of an adverse event is on 09-Jan-2014 then the study day of the adverse event onset is day 5. For safety assessments before start of study treatment, the study day is negative and derived by (date of event – start date of study treatment). For example: if start of study treatment is on 05-Jan-2014 and date of lab measurement is on 02-Jan-2014 then the study day of the laboratory abnormality is -3. Note, the day of start of study treatment is day 1, and the day before the date of first study treatment is day – 1, not day 0.

The study day will be displayed in the data listings.

### **Baseline**

The results of any specified study assessments performed on the day of the Transition Visit will serve as the baseline value for the said assessment. On-treatment assessment/event and observation periods

Adverse events, serious adverse events, death will be assigned to the treatment periods defined below. Flag variables indicating the treatment period will be added to these datasets.

#### **1. Pre-treatment period:** prior to start of eltrombopag

**2. On-treatment period:** from start of eltrombopag to last dose date of eltrombopag + 30 days  
It is noted that if patient withdraws study informed consent or dies before then, then it is till the withdrawal/death date

**3. Post-treatment** from last dose date of eltrombopag + 31 days to end of study

If dates are incomplete in a way that clear assignment to on-, post-treatment period cannot be made, then the respective data will be assigned to the on-treatment period.

Safety summaries (tables, figures) include only data from the on-treatment period with the exception of baseline data which will also be summarized where appropriate (e.g. change from baseline summaries). In addition, a separate summary for death including on treatment and all deaths will be provided. Summary tables for adverse events (AEs) will summarize only on-treatment events, with a start date during the on-treatment period (**treatment-emergent** AEs).

However, all safety data (including those from the pre and post-treatment period) will be listed and those collected during the post-treatment period will be flagged.

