#### 3.2.4. Visit Schedule for Cohort A, Cohort B, and Cohort C

**Figure 1 Visit Schedule**

1. For Cohort B and Cohort C, more frequent visits may be required (Section 5.4.2.3.)

Subjects in **Cohort A, Cohort B and Cohort C** will complete the Transition Visit assessments (Section 8.1.) and then return for their next scheduled visit in 2 weeks, or

sooner if the visit schedule in the parent study had been more frequent than every two weeks (e.g. weekly schedule). Subjects who have been on a stable dose of eltrombopag for the previous 2 every two week visits may decrease the frequency of visits to once monthly visits. Subjects who are stable on a monthly dose for the previous 3 monthly visits may decrease the frequency of visits to once every 2 months. If any change in the study treatment dose is required, the schedule of visits must begin again with weekly visits for at least 4 weeks, followed by biweekly, then monthly and then bimonthly visits (See schematic in Figure 1).

Once treatment with eltrombopag is permanently discontinued, the subject will attend the follow up visit as per Appendix 1. If there are any uncertainties about the dose(s) of study treatment(s) to be administered or the visit schedule, the Novartis Medical Lead should be consulted.

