#### **5.4.1.3. Dose Interruption**

Temporary interruptions of study medication may be made by the investigator (e.g. to allow for recovery of AEs).

Refer to Section 4.2.1 for criteria for permanent discontinuation of study medication.

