#### **8.4.5. Time Period and Frequency of Detecting AEs and SAEs**

The investigator or site staff is responsible for detecting, documenting and reporting events that meet the definition of an AE or SAE.

AEs will be collected from the time of ICF signature until 30 days following discontinuation of study treatment regardless of initiation of a new cancer therapy or transfer to hospice.

SAEs will be collected over the same time period as stated above for AEs. In addition, any SAE assessed **as related** to study participation (e.g., protocol-mandated procedures, invasive tests, or change in existing therapy), will be reported promptly to Novartis within 24 hours, as indicated in Section 8.4.7.

After discontinuation of study treatment, the investigator will monitor all AEs/SAEs that are ongoing until resolution or stabilization of the event or until the subject is lost to follow-up. At any time after 30 days the investigator may report any adverse event that they believe possibly related to study treatment.

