### **2.7.1 Adverse events (AEs)**

Summary tables for adverse events (AEs) will include only AEs that started or worsened during the on-treatment period, the *treatment-emergent* AEs.

AEs will be summarized by number and percentage of subjects having at least one AE, having at least one AE in each primary system organ class (SOC) and for each preferred term (PT) using the latest version of the medical dictionary for regulatory activities (MedDRA) at the time of the analysis for coding. A subject with multiple occurrences of an AE will be counted only once in the respective AE category. A subject with multiple CTCAE grades for the same preferred term will be summarized under the maximum CTCAE grade recorded for the event.

In AE summaries, the primary system organ class (SOC) will be presented alphabetically and the preferred terms (PT) will be sorted within primary SOC in descending frequency. The sort order for the preferred term will be based on descending frequency.

The following AE summaries will be produced:

- All AEs regardless of relationship to study treatment by primary system organ class (SOC), preferred term (PT) and maximum severity
  - In-text table by SOC and maximum severity
  - In-text table by PT and maximum severity
- AEs suspected to be related to study treatment by SOC, PT and maximum severity
  - In-text table by PT and maximum severity
- AEs leading to treatment discontinuation regardless of relationship to study treatment by SOC, PT and maximum severity
  - In-text table by PT and maximum severity
- Serious AEs (SAEs) regardless of relationship to study treatment by SOC, PT and maximum severity
  - In-text table by PT and maximum severity
- On-treatment deaths by SOC and PT
  - In-text table by PT
- \*Non-SAEs regardless of relationship to study treatment (threshold=x%) by SOC and PT
- \*On treatment deaths and SAEs by SOC and PT

\*For the legal requirements of EudraCT, two required tables on on-treatment/treatment emergent AEs which are not SAEs with an incidence greater than x% and on on-treatment/treatment emergent SAEs and SAE suspected to be related to study treatment will be provided by SOC and PT on the ATS.

If for a same patient, several consecutive AEs (irrespective of study treatment causality, seriousness and severity) occurred with the same SOC and PT:

- a single occurrence will be counted if there is  $\leq 1$  day gap between the end date of the preceding AE and the start date of the consecutive AE

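### A new AE starting more than 30 days into an interruption that is never resumed is left out of the AE tables, including the table of AEs leading to discontinuation

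*SAP*

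**What the plan says.** SAP 2.1.1 sets the on-treatment period as "from start of eltrombopag to last dose date of eltrombopag + 30 days", cut short by death or withdrawal of consent. The post-treatment period runs "from last dose date of eltrombopag + 31 days to end of study". The anchor is defined in the same section: "The date of last administration of study drug is defined as the last date when a non-zero dose of study drug was administered". Days at zero dose do not move it.

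SAP 2.1.1 and 2.7.1 restrict the AE summary tables to on-treatment events. Post-treatment events appear in listings with a flag. One of the restricted tables is "AEs leading to treatment discontinuation regardless of relationship to study treatment by SOC, PT and maximum severity". SAP 2.3.1 separately tabulates the primary reason for end of treatment from the discontinuation page of the eCRF, and states no limit on time since last dose.

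On the protocol side, section 5.4.1.3 allows interruptions in Cohort A ("Temporary interruptions of study medication may be made by the investigator") and gives no maximum length. Section 5.4.2.3 ends an ITP interruption on a platelet count, again with no time limit. Section 8.4.5 states: "AEs will be collected from the time of ICF signature until 30 days following discontinuation of study treatment". Section 10.3.4 includes all data up to study completion or withdrawal. Section 10.3.4.1.1 plans a summary of AEs leading to discontinuation and does not limit it by time since last dose.

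**The concern.** During an interruption nobody yet knows whether the most recent dose was the final one. Under the SAP rule, a new AE that appears late in the interruption is classified by what happens afterwards: on-treatment if dosing resumes, post-treatment if it does not. The AE itself can decide which. The effect runs one way, because late-onset events that end treatment leave the tables and late-onset events followed by a restart stay in.

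The consequence is plainest in the discontinuation-AE table, whose purpose is to show the events that ended treatment. A subject whose treatment ended because of such an event can appear under AE as reason for stopping in the disposition table and be absent from the discontinuation-AE table. The report would then hold two different counts with no stated reason. SAP 2.5 names safety as the primary objective, so these are main tables.

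**Working it through.** There is no plan figure to reproduce. This is a check of a date rule.

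**Inputs**
- On-treatment if first dose ≤ onset ≤ L + 30 days, where L is the date of the last non-zero dose (SAP 2.1.1).
- Post-treatment from L + 31 days (SAP 2.1.1).
- Number analysed: 22 (SAP section 1). Cohort sizes are not given.

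**Rule with and without a restart.** Let S be the last dose before the interruption and k the days from S to the onset of a new AE.
- No restart: L = S, so the AE is on-treatment only if k ≤ 30.
- Restart with one dose five days after onset (illustrative): L = S + k + 5. The period then runs to S + k + 35, so the AE is on-treatment for any k.

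| k (days after last dose) | Never resumed | One later dose |
|---|---|---|
| 10, 20, 30 | on-treatment | on-treatment |
| 31, 40, 60, 90 | post-treatment | on-treatment |

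The switch is exactly at day 31. The treatment of exposure agrees with this: "The duration includes periods of temporary interruption (planned or actual) for any reason", but that duration ends at the last dose, so only an interruption followed by a further dose lies inside it.

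**Does another provision bring the event back?**
- SAP 2.1.1 refers to AEs with a start date in the period, and 2.7.1 to AEs that started or worsened in it. Neither admits an AE that first starts after L + 30.
- Dates too incomplete to assign go to on-treatment, which does not help an AE with a known date.
- All deaths have their own summary, so a fatal event is still counted as a death.
- The AE listing shows the event with a flag.

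**Disposition against the discontinuation-AE table.** Take k = 45, with the AE recorded as the reason for permanent discontinuation. Disposition (SAP 2.3.1) counts 1. The discontinuation-AE table (SAP 2.7.1) counts 0, because 45 > 30.

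**Size of one lost subject**
- All 22: 1/22 = 4.5 percentage points.
- Tables are by cohort. Assuming a cohort of 11: 1/11 = 9.1 points. Assuming 5: 1/5 = 20.0 points.

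**The case against.** Last dose + 30 days is a reasonable safety window, and the protocol uses the same anchor for follow-up: section 8.3 and Appendix 1 both time the final visit from the last study treatment. That stands, and it is a good reason not to redefine the whole on-treatment period. Extending the period for some subjects would give them a longer off-drug window than others, and the documents do not clearly identify a decision date separate from the last dose.

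Three stronger readings are tempting, and the documents do not support them.
- *Any AE that prevents a restart is lost.* Not so. The rule works on AE onset. An AE that led to the interruption normally began on drug, and any AE starting within 30 days of the last dose stays in the tables however late the stop is decided.
- *The frequency of lost events can be estimated from the visit schedule, since stable subjects "may decrease the frequency of visits to once every 2 months".* A gap between visits bears on when a stop is decided, not on when an AE starts. It also overlooks closer observation: protocol 3.2.4 returns subjects to weekly visits after a dose change (it does not say whether an interruption counts as one), and 5.4.2.3 requires platelet checks up to twice weekly during prolonged ITP interruptions.
- *The SAP contradicts the protocol's collection window.* Section 8.4.5 counts from discontinuation of treatment, which may mean the permanent stop, but other sections count from the last dose. The wording is too loose to establish a contradiction.

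It is also fair to say that the study is descriptive, and that with 22 subjects a reader can find each flagged event in the listing. That limits the harm. It does not explain why two tables in one report should disagree on who stopped for an AE.

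**Conclusion.** The point holds in a narrow form. A new AE starting 31 or more days after the last non-zero dose, in an interruption that is never resumed, is left out of the AE summary tables, while the same AE followed by a restart is counted. Where that AE is the cause of permanent discontinuation, the discontinuation-AE table omits it although disposition can count it. Protocol 10.3.4 and 10.3.4.1.1 set no such limit, and SAP section 4 does not record one as a change.

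The number of such events is not given and may be zero, since the documents report no interruption lengths. Each one would shift an incidence by 4.5 points across all 22 subjects. The within-cohort figures of 9.1 and 20.0 points rest on assumed cohort sizes. The conclusion on the two tables assumes that the late AE is recorded in the database and marked as the reason for stopping.

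**What to change.** In SAP 2.7.1, build the discontinuation-AE table from every AE with onset on or after the first dose that is recorded as the cause of permanent discontinuation, whatever the time since last dose. Events that 2.7.1 already admits through worsening on treatment should stay in. Show days since last dose in the AE listing. Record the rule in SAP section 4. Keep last dose + 30 days as the general on-treatment period for all other summaries.

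The cost is a few lines of SAP text, one selection rule for one table and one derived listing column. The rule uses the recorded cause of discontinuation, so it needs no separate decision date. The downside is that an occasional event well after the last dose enters that one table, where days since last dose will identify it. If no event qualifies, the table does not change.

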## 6 Appendix

### 6.1 Imputation rules

**Table 6-1 Imputation of start dates (AE)**

Missing Element	Rule
day, month, and year	
 
• No imputation will be done for completely missing dates
 

day, month	
 
• If available year = year of study treatment start date then 
 
◦ If stop date contains a full date and stop date is earlier than study treatment start date then set start date = 01JanYYYY
 
◦ Else set start date = study treatment start date.
 
 
 
• If available year > year of study treatment start date then 01JanYYYY
 
• If available year < year of study treatment start date then 01JulYYYY
 

day	
 
• If available month and year = month and year of study treatment start date then 
 
◦ If stop date contains a full date and stop date is earlier than study treatment start date then set start date= 01MONYYYY.
 
◦ Else set start date = study treatment start date.
 
 
 
• If available month and year > month and year of study treatment start date then 01MONYYYY
 
• If available month and year < month year of study treatment start date then 15MONYYYY
 

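### SAP 2.1.1 and 2.7.1 define treatment-emergent AEs differently, and Table 6-1 can date an AE already known to be ongoing at transition to study day 1

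*SAP*

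**What the plan says.** SAP 2.1.1 sets up three periods: before first dose, on treatment (first dose to 30 days after last dose, cut short by death or withdrawal of consent), and after. "Adverse events, serious adverse events, death will be assigned to the treatment periods defined below". It then fixes the content of the AE tables: "Summary tables for adverse events (AEs) will summarize only on-treatment events, with a start date during the on-treatment period". SAP 2.7.1 says that the same tables "will include only AEs that started or worsened during the on-treatment period". Both sections call the result treatment-emergent.

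SAP Table 6-1 governs incomplete AE start dates.
- **Known part matches first dose** (same year, or same month and year): the start becomes the first of that year or month if a full stop date precedes first dose. Otherwise: "Else set start date = study treatment start date".
- **Known part is earlier than first dose:** the date goes to 1 July of that year, or to mid-month ("month year of study treatment start date then 15MONYYYY").
- **Known part is later than first dose:** the date goes to the first day of that year or month.
- **Nothing known:** "No imputation will be done for completely missing dates".

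SAP 2.1.1 also has a default, which opens "If dates are incomplete in a way that clear assignment to on-, post-treatment period cannot be made" and sends such data to the on-treatment period.

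The protocol foresees AE records from before first dose. Section 8.4.5 says: "AEs will be collected from the time of ICF signature until 30 days following discontinuation of study treatment". Section 8.1 requires AEs ongoing at transition to be documented, and footnote 1 of Appendix 1 requires all Transition Visit procedures to be finished before first dose.

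**The concern.** Safety is what this study reports, and the AE tables rest on the treatment-emergent rule. One term has two definitions, so two programmers working from the same SAP could build different tables.

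The imputation rule raises a separate question. Dating an uncertain onset to day 1 is a common cautious choice when nothing else is known about timing. In a rollover study something else is known: an AE documented as ongoing at the Transition Visit was present before first dose. Table 6-1 makes no use of that fact. Its only protection is an earlier full stop date, which an ongoing AE cannot have. A condition carried over from the parent study could therefore appear as a new event on day 1.

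The summary table would not show this. The listings flag records outside the on-treatment period, but the SAP does not say whether the flag uses the recorded or the imputed date. If it uses the imputed date, the moved AE carries no flag.

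**Working it through.** **1. The two wordings.** An AE starting on treatment is counted under both. An AE starting earlier and not worsening is counted under neither. An AE starting earlier and worsening on treatment is counted under both if the worsening is a new record with its own start date. If the grade is raised on the original record, only 2.7.1 counts it. Protocol 8.4.4.1 makes an increase in grade of a pre-existing condition an AE, but no section says how it is recorded. Protocol 8.4.7 leaves recording methods to the Study Procedures Manual.

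**2. Table 6-1 on an illustrative case.** Take first dose on 15 June 2014 and an AE still ongoing.

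| True onset | Day missing | Day and month missing |
|---|---|---|
| 10 June 2014 | 15 June 2014, day 1 | 15 June 2014, day 1 |
| 2 March 2014 | 15 March 2014, day -92 | 15 June 2014, day 1 |
| 2 November 2013 | 15 November 2013, day -212 | 1 July 2013, day -349 |

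The move to day 1 happens only when the known part of the date matches first dose. Full dates, and partial dates in an earlier month or year, stay pre-treatment.

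**3. How often a partial date would be moved.** Assume no stop date before first dose, and first doses spread evenly over a 365-day year. With the day missing, an onset L days earlier moves when the first-dose day of the month exceeds L. For L up to 28 that is 365 - 12L dates. With day and month missing it is 365 - L dates.

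| L (days) | Day missing | Day and month missing |
|---|---|---|
| 7 | 281/365 = 77.0% | 358/365 = 98.1% |
| 14 | 197/365 = 54.0% | not tabulated |
| 28 | 29/365 = 7.9% | 337/365 = 92.3% |
| 31 | 0% | not tabulated |
| 180 | 0% | 185/365 = 50.7% |
| 365 | 0% | 0% |

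These shares are conditional on a partial date. The documents do not say how many AEs have one.

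**4. Direction.** An on-treatment onset in the first-dose month or year is set to first dose, which is on treatment. One in a later month or year is set to the first of that month or year, which is after first dose and no later than the true onset, so it is also on treatment. Enumeration agrees. I took five first-dose dates, five durations from 1 to 1,500 days, both missing patterns and five stop-date options. None of the 2 x (43,220 + 10,805) = 108,050 on-treatment cases left the period. All moves were pre to on or post to on.

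Occurrence counts behave differently. For the EudraCT tables, SAP 2.7.1 merges consecutive AEs of the same term when the gap is at most one day. Suppose one AE ends on 5 August and the next truly starts on 20 August with the day missing. The second is imputed to 1 August, and the two become one occurrence.

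**5. Effect on a table row.** The SAP Introduction gives 22 subjects, so one added subject is 1/22 = 4.5 points pooled. SAP 2.7 displays by cohort, and SAP 2.1 says Cohort C is empty. The split is not given. If both remaining cohorts have subjects, the larger has 11 to 21 (1/21 = 4.8 to 1/11 = 9.1 points). The smaller has at most 11 (9.1 points or more). The effect is zero if the subject is already in that row.

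**The case against.** **The wording mismatch may be editorial.** The protocol's AE definition, and the SAP's rules for consecutive AEs and for several grades of one term, fit a one-record-per-worsening practice. Section 2.7.1 is also the more specific text for AE tables. This stands as a reason to rate the point low. It does not remove the mismatch, because no section requires that practice.

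**Day-1 imputation is cautious, and several conditions must coincide.** The event must be held as an AE record rather than as a current medical condition at baseline, its date must be partial, and the known part must match first dose. All of that is fair. But caution about unknown timing does not justify overriding timing that the trial has documented.

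**A reader might infer that AEs with no start date have no rule at all.** The documents do not support that. The 2.1.1 default names only the on- and post-treatment periods, but an AE that cannot be clearly placed in either meets its literal condition and goes to on-treatment. What is missing is an explicit mention of the pre-treatment period, which is a matter of clarity.

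**A reader might also infer that Table 6-1 inflates every AE count.** It can only inflate the treatment-emergent flag and subject counts. Occurrence counts can also fall through merging.

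**Conclusion.** The point holds, and its priority is minor. The two SAP sections differ for one kind of AE: onset before the first rollover dose, worsening kept on the original record. There the 2.1.1 wording omits an event that 2.7.1 includes. Table 6-1 can make an AE documented as ongoing at transition treatment-emergent, provided that it is held as an AE record with a partial start date matching first dose. The two faults pull in opposite directions, so the net direction cannot be stated.

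The percentages in the working show where the rule bites: roughly the month before dosing when the day is missing, and up to a year when the month is missing too. They do not estimate bias in this study, and nothing in the documents shows that any reported incidence is wrong. The study tests no hypotheses and makes no comparisons. Partial and missing dates appear in the listings as recorded, so a case can be traced.

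**What to change.** - Use the started-or-worsened rule in both SAP 2.1.1 and 2.7.1. Define worsening in one line: a CTCAE grade above that held before the first rollover dose, or a new record for the worsening.
- Add to Table 6-1 that an AE documented as ongoing at the Transition Visit, with a partial or missing start date, is pre-treatment and is counted only if it worsens on treatment. Impute a partial date no later than the day before first dose.
- If Transition Visit documentation cannot be linked to the AE data, check by hand the AEs imputed to day 1 before database lock, and footnote those that pre-existed.
- Optionally, name the pre-treatment period in the 2.1.1 default, so that it plainly covers any other AE with no start date. This is clarification only.

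The cost is a few lines of SAP text and a little programming, or a short manual check over 22 subjects. The definition of worsening needs the grade before first dose. If that is not held, rely on new records. No change to data collection or clinical conduct is involved.
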